# 3. ENDPOINTS AND BASELINE VARIABLES: DEFINITIONS AND CONVENTIONS

## 3.1. Primary Endpoint(s)

#### 3.1.1. Primary Safety Endpoints

Primary safety endpoints include both reactogenicity data collected from the e-diary and AE data collected from the CRF.

Based on feedback from the FDA on multiple vaccine programs, reactogenicity data will utilize both e-diary data (prompted local reactions and systemic events) and reactogenicity events (related or unrelated) reported in the AE CRF during the e-diary collection period. Since the AE CRF does not designate a specific page to collect reactogenicity data for an untransmitted e-diary, Pfizer has adopted a process of providing a listing of AEs reported within 7 days after vaccination to the clinical team to review and determine ("flag") which

PTs should be considered reactogenicity events before the database lock. AEs reported on the same day of vaccination but missing a start time are defaulted to AEs reported after vaccination. Following these review steps, those AEs reported within 7 days after vaccination that match flagged PTs (either related or unrelated) will be considered reactogenicity data. If the same reactogenicity event is reported on the same day from both the e-diary and the AE CRF, the highest grade from the 2 data sources will be used for that specific day for analysis.

It should be noted that the data collection in the AE CRF is different from that of the e-diary:

- For redness, swelling, and fever, the measured size of redness and swelling at the injection site and temperature are recorded in the e-diary, but not in the AE CRF. As the missing e-diary entries are monitored with ongoing review of the prompted reactions reported in the AE CRF, any measurement recorded in the query response will be taken into consideration for the primary analysis using the data handling memo for analysis purposes. For the 7 days, only the maximum grading from both sources will be used for the aggregated severity analysis.
- For pain at the injection site and all other systemic events, the severity grading algorithm for the e-diary data and the AE CRF may not be the same. Pfizer will choose the highest-severity grade.

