If a participant did not have any e-diary data transferred within 7 days after vaccination, the AE CRF data will not be used for derivation, because doing so may inflate the denominator and bias the analysis, since participants who did not transfer e-diary data may be less likely to report reactogenicity data. If a participant did not report any e-diary data, the participant will not be included in the analysis of reactogenicity data.

The subsections below describe how to derive each safety endpoint.

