#### 3.1.1.3. Adverse Events and Serious Adverse Events

Standard algorithms for handling missing AE dates and missing AE severity will be applied as described in the Pfizer vaccine data standard rules. Completely missing AE start dates will not be imputed.

The following derivations will be included for each participant:

- 1. Any AE reported within 1 month after vaccination If the AE started on the same day of vaccination, if the AE start time is before the vaccination time, this AE would not be counted. Otherwise, if the AE start time is missing or after the vaccination time, the AE is included. Any AE reported after the 1-month visit will not be included in the analysis.
- 2. Any related AE reported within 1 month after vaccination Similar to above except only a related AE is included (but excluding related reactogenicity reported within 7 days of vaccination) (Section 3.1.1).
- 3. Any immediate AE (AE start time is within 30 minutes after vaccination) reported after vaccination Only include AEs that started on the same day of vaccination and with nonmissing AE start time that is within 30 minutes of vaccination. If the immediate AE is a related reactogenicity event, this would not be included as an immediate AE.
- 4. Any severe AE reported within 1 month after vaccination.
- 5. Any life-threatening AE reported within 1 month after vaccination.
- 6. Any AE leading to study withdrawal after vaccination.
- 7. Any SAE reported throughout the study.
- 8. Any NDCMC reported throughout the study.
- 9. Any AESI reported throughout the study.

Variables 1 through 6 listed above will be derived from excluding any reactogenicity (but not excluding reactogenicity SAEs) reported in the AE CRF during the e-diary collection period. AESIs are flagged in the CRF.

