## 3.4.3. E-Diary Completion

An e-diary will be considered transmitted if any data for the local reactions and systemic events are present for any day. If all data are missing for all items (local reactions and systemic events) on the e-diary for all 7 days after vaccination, then the e-diary will be considered not transmitted. An e-diary will be considered transmitted for a given day if any data are present for that day.

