#### 5.3.1.1. Reactogenicity Data

For derived variables based on the reactogenicity data, if any day of the 7-day e-diary is available, the "any day (Days 1-7)" data will be considered nonmissing.

The reactogenicity data are collected in the e-diary, which does not allow participants to skip any questions. Therefore, for a specific day, if the e-diary data are transferred for that day, all of the reactogenicity data for the participant on that day are nonmissing. In general, for any participant with all 7 days of the e-diary data missing, this participant will not be included in the analysis (ie, assuming MCAR). If only 1 through 6 days of e-diary data are transferred, it is expected that any missed reactogenicity events would be entered in the AE CRF if any experienced reactogenicity was not reported in the e-diary due to missed days. Therefore, the primary analysis will use reactogenicity recorded in the AE CRF to impute the partially missed e-diary data to estimate the reactogenicity rate during the e-diary collection period. The AE CRF is designed as a log page, which means only events that occurred will be recorded and events that did not occur will not be recorded. Therefore, all remaining missing days are considered as "no." This imputation can reasonably estimate the reactogenicity event rates during the e-diary collection period.

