#### 6.1.2.1. Main Analysis

- Estimand strategy: Treatment policy (Section 2.2.1.1.2).
- Intercurrent events and missing data: All data collected are included.
- Analysis set: Safety population (Section 4).
- Analysis timing: At primary analyses (when all primary endpoint data are available).
- Analysis methodology: 95% CIs of the proportion of participants reporting those events will use the Clopper-Pearson method (Section 5.2.1).
- Descriptive statistics, including the proportion (%), the numerator (n) and the denominator (N) used in the proportion calculation, and the 95% CI for percentage using the Clopper-Pearson method, will be presented for each vaccine group for each analysis interval (Section 5.2.1).
- Bar charts with the proportions of participants for each variable within the specified interval will be plotted for each group. The bars may be divided into relatedness categories to highlight the proportions of participants with related events.
- The main analysis will be based on AEs and will exclude the reactogenicity events that were reported in the AE CRF (except for SAEs) (Section 3.1.1.3).

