#### **6.1.2.3. Sensitivity Analysis of AEs**

In addition, a sensitivity analysis will be conducted using all AEs (not excluding the reactogenicity events reported in the AE CRF during the e-diary collection period).

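### A non-serious reaction in a vaccinated child with no e-diary data is counted in neither main primary safety analysis

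*SAP*

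**What the plan says.** **Flagging.** SAP 3.1.1 has the clinical team review AEs with onset in the first week and flag preferred terms before database lock. After that, "those AEs reported within 7 days after vaccination that match flagged PTs (either related or unrelated) will be considered reactogenicity data". No condition on e-diary transfer is attached. The reason given for the process begins: "Since the AE CRF does not designate a specific page to collect reactogenicity data for an untransmitted e-diary". SAP 3.4.3 covers a diary with every item missing "on the e-diary for all 7 days after vaccination, then the e-diary will be considered not transmitted".

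**Reactogenicity analysis.** For a child with no diary data, SAP 3.1.1 bars use of the AE CRF in the derivation and adds: "If a participant did not report any e-diary data, the participant will not be included in the analysis of reactogenicity data". The stated reason is that including such children could inflate the denominator and bias the rate. SAP 5.3.1.1 repeats the rule for a child with all 7 days missing: "this participant will not be included in the analysis (ie, assuming MCAR". SAP 6.1.1.1 restricts the calculation to children with at least one day transferred.

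**AE analysis.** SAP 3.1.1.3 closes with: "Variables 1 through 6 listed above will be derived from excluding any reactogenicity (but not excluding reactogenicity SAEs) reported in the AE CRF". Those six variables are any, related, immediate, severe and life-threatening AEs, and AEs leading to withdrawal. SAP 6.1.2.1 says the main analysis "will exclude the reactogenicity events that were reported in the AE CRF (except for SAEs". Its analysis set is the whole safety population.

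**Sensitivity analyses.** For reactogenicity (SAP 6.1.1.3), e-diary data only. For AEs (SAP 6.1.2.3), "a sensitivity analysis will be conducted using all AEs (not excluding the reactogenicity events reported in the AE CRF during the e-diary collection period".

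**The concern.** Each exclusion makes sense alone. Dropping no-diary children from the reactogenicity rate protects its denominator. Dropping CRF reactogenicity from the AE rate stops one reaction being counted in two tables. The difficulty is that both apply to the same child. With no diary there is nothing to double count, yet the event is still removed from the AE table, and the child remains in that denominator as a non-event if there is no other AE. The error runs one way, towards fewer AEs.

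The protocol makes such records likely to exist. Protocol 8.12 requires sites to contact families who are not completing the diary and obtain details of missed events. Protocol 8.3 and 8.10.1 send acute reactions in the first 30 minutes to the AE page regardless of the diary.

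Safety and tolerability is the primary objective and groups hold about 20 children, so a single event is visible in a table. The variables at risk are any, related, immediate and severe AEs. SAEs, NDCMCs and AESIs are outside the exclusion. Life-threatening AEs would normally be SAEs and so are kept.

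**Working it through.** The plan states no figure on this point, so there is nothing to reproduce. The check is a rule trace followed by an illustration of size.

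**1. Rule trace** for an AE within 7 days matching a flagged term:

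| Diary days transferred | Event | Main reactogenicity | Main AE | E-diary-only sensitivity | All-AE sensitivity |
|---|---|---|---|---|---|
| 0 | non-serious | no | **no** | no | yes |
| 0 | serious | no | yes | no | yes |
| 1 or more | non-serious | yes | no | CRF record not used | yes |
| 1 or more | serious | yes | yes | CRF record not used | yes |

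Only the first row is missing from both main analyses. The supplementary AE summaries in SAP 6.1.2.2 use the same variables from 3.1.1.3, so they do not recover it.

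**2. Effect of one event on a table.** Group size is about 20 (SAP 2.3). Intervals are two-sided 95% Clopper-Pearson, as planned: lower = Beta quantile(0.025; x, n − x + 1), upper = Beta quantile(0.975; x + 1, n − x). With x = 0 the lower limit is 0 and the upper is 1 − 0.025^(1/n).

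| Situation | Main AE result as written | Event retained |
|---|---|---|
| One affected child, no other AE in the group | 0/20 = 0% (0 to 16.8%) | 1/20 = 5.0% (0.1 to 24.9%) |
| One affected child, 4 of the other 19 have an AE | 4/20 = 20% (5.7 to 43.7%) | 5/20 = 25% (8.7 to 49.1%) |

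In the first situation the main reactogenicity table shows 0/19 (0 to 17.6%), so neither main table shows the event.

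**3. How often, under assumptions.** Let p be the share of children transmitting no diary, and r the share of those with a non-serious flagged event in the CRF and no other AE. Neither is in the documents.

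- Average lowering of the any-AE percentage = p × r.
- Chance that at least one child is affected = 1 − (1 − p × r)^N, with N = 60 or 120 (the planned enrolment range).
- Expected affected children in a group of 20 = 20 × p × r.

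| p | r | Lowering (points) | At least one, N = 60 | At least one, N = 120 | Expected per group of 20 |
|---|---|---|---|---|---|
| 0.02 | 0.10 | 0.2 | 11% | 21% | 0.04 |
| 0.05 | 0.20 | 1.0 | 45% | 70% | 0.2 |
| 0.10 | 0.30 | 3.0 | 84% | 97% | 0.6 |

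The condition of no other AE fits the any-AE variable. The related, immediate and severe variables are not quantified here.

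**The case against.** The strongest reply is that this is a silence in the text. SAP 3.1.1 says a no-diary child's CRF data are not used in the reactogenicity derivation, and a programmer might infer that an event not used as reactogenicity reverts to being an ordinary AE. That may be the intent, but no section says so, and the closing sentence of 3.1.1.3 read as written removes the event.

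Other points stand in part:

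- The word for an untransmitted diary in SAP 3.1.1 could refer to missed days, since 3.4.3 also defines transmission for a given day. That weakens the inference about why flagging was introduced. The flagging rule still carries no diary condition.
- Items 2 and 3 of SAP 3.1.1.3 (related and immediate AEs) mention only related reactogenicity, whereas the closing sentence covers any. On the item wording, an unrelated immediate event would stay. The two need to agree.
- Protocol Table 5, which plans to summarize all AEs within 1 month, is limited support: read literally it would also oppose the exclusion for children with diaries. It does show that the protocol does not call for this loss.
- The event is not hidden. It is in the CRF, open to IRC and stopping-rule review, and in the all-AE sensitivity analysis; diary completion is also summarized. However, that sensitivity analysis restores CRF reactogenicity for every child, so it cannot isolate this case or correct the main table.
- The size rests on assumptions, and SAP 3.1.1 itself suggests non-transmitters may report less, which argues against the upper end. The intervals in the examples overlap heavily, and no hypothesis test depends on the result.

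**Conclusion.** The point holds. As written, a non-serious flagged-term AE within 7 days in a vaccinated child with no e-diary data is left out of both main primary safety analyses and appears only in the all-AE sensitivity analysis. The reason given for excluding the child concerns the reactogenicity denominator and does not extend to the AE analysis, where the child is already in the denominator.

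The direction is certain: AE percentages can only be lowered. The size is not known. One event moves a group of 20 by 5 percentage points, and the average lowering is 0.2 to 3.0 points under the assumed ranges. The issue should be fixed before the analysis, but it does not affect serious events or ongoing safety review.

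A smaller matter is that the same exclusion covers AEs leading to study withdrawal, so a non-serious reaction that caused a withdrawal would not be counted there. The withdrawal and its reason are still tabulated under SAP 6.5.2.

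**What to change.** In the last paragraph of SAP 3.1.1.3 and the last bullet of 6.1.2.1, add two sentences to this effect: *The exclusion applies only to participants in the e-diary safety population, that is, to events used in the reactogenicity derivation. For vaccinated participants with no e-diary data transferred, AEs matching flagged terms within 7 days stay in variables 1 through 6 and are footnoted.* Align items 2 and 3 of 3.1.1.3 with the closing sentence on whether related or any reactogenicity is meant. As a secondary change, exempt variable 6 (AE leading to withdrawal) from the exclusion.

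The cost is the added text and one programming condition on an analysis set already defined in SAP Section 4. The reactogenicity analysis is unchanged and nothing is counted twice. The downside is that AE totals will contain reactogenicity terms for no-diary children but not for others in the same column, so the rate depends slightly on diary compliance. The footnote lets a reader separate them.

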## 3.1.1.1. Local Reactions Within 7 Days After Vaccination

The local reactions include redness, swelling, and pain at the injection site from Day 1 through Day 7 after vaccination, where Day 1 is the day of vaccination with RSVpreF. Any reported reactogenicity events in the AE CRF during the e-diary collection period are included in the derivation discussed below.

The following section describes derivations with details for the assessment of local reactions: any presence, maximum severity, duration, and onset day of local reactions, in addition to presence of local reactions on each day, for each vaccine group as mentioned above.

#### 3.1.1.1.1. Presence of Local Reactions Within 7 Days After Vaccination

For the summary of the presence (yes or no) of a local reaction during the interval from Day 1 through Day 7 after vaccination, the following 2 variables are derived for each participant included in the reactogenicity subset:

1. Presence (yes or no) of each local reaction on any day (Day 1 through Day 7).

The derivation is described in Table 2.

**Table 2.** Derived Variables for Each Local Reaction

Variable a	Yes (1)	No (0)	Missing (.)
Any day (Days 1-7)	The participant reports the reaction as "yes" on any day (Days 1-7).	reaction as "no" on all 7 days	The participant reports the reaction as missing on all 7 days.

a. The variable will be defined for each of the 3 local reactions.

2. Presence (yes or no) of any local reaction on any day (Day 1 through Day 7).

For any local reaction on any day, a similar definition can be applied as given in Table 3.

**Table 3.** Derived Variables for Any Local Reaction

Variable	Yes (1)	No (0)	Missing (.)
Any day (Days 1-7)	The participant reports any local reaction as "yes" on any day (Days 1-7).	reactions as "no" on all 7 days	The participant reports all local reactions as missing on all 7 days.

## 3.1.1.1.2. Maximum Severity of Local Reactions Within 7 Days After Vaccination

The grading of local reactions is listed in Table 4.

**Table 4.** Grading Scale for Local Reactions

	Mild Grade 1	Moderate Grade 2	Severe Grade 3	Grade 4 a
Redness	Mild grading from the e-diary per Table 2 in the protocol or mild from the AE CRF	Moderate grading from the e-diary per Table 2 in the protocol or moderate from the AE CRF	Severe grading from the e-diary per Table 2 in the protocol or severe from the AE CRF	Necrosis or exfoliative dermatitis
Swelling	Mild grading from the e-diary per Table 2 in the protocol or mild from the AE CRF	Moderate grading from the e-diary per Table 2 in the protocol or moderate from the AE CRF	Severe grading from the e-diary per Table 2 in the protocol or severe from the AE CRF	Necrosis

	Mild Grade 1	Moderate Grade 2	Severe Grade 3	Grade 4ª
Pain (at the injection site)	Does not interfere with activity (mild from the e-diary or AE CRF)	Interferes with activity (moderate from the e-diary or AE CRF)		Emergency room visit or hospitalization for severe pain at the injection site

**Table 4.** Grading Scale for Local Reactions

The following variables are derived for each participant:

1. Maximum severity of each local reaction on any day (Day 1 through Day 7).

The maximum severity (highest grading) of each local reaction within 7 days after vaccination will be derived. The maximum severity will be derived as follows:

- = Missing, if values are missing for all days (Days 1-7);
- = 0, if the participant reports all reactions as "no" or a combination of missing and "no" for all days (Days 1-7);
- = Highest grade (maximum severity either from the e-diary or in the AE CRF) within 7 days after vaccination if the answer is not "no" for at least 1 day.
- 2. Maximum severity of any local reaction on any day (Day 1 through Day 7).

The maximum severity for any local reaction will be derived as follows:

- = Missing, if values are missing for all days (Days 1-7) across all 3 local reactions;
- = 0, if the participant reports all reactions as "no" or a combination of missing and "no" for all days (Days 1-7) for all individual local reactions;
- = *Highest grade* (maximum severity) within 7 days after vaccination, if the answer is not "no" for at least 1 day for at least 1 local reaction.

#### 3.1.1.3. Duration of Each Local Reaction

The duration of each local reaction will be calculated in days as the resolution date of reaction - start date of reaction + 1. Resolution of the event is the last day on which the event is recorded in the e-diary (or AE CRF) or the date the event ends if it is unresolved during the participant e-diary recording period (end date collected on the CRF) or AE stop date, whichever is longer, unless chronicity is established.

If there is no known end date, the duration will be considered unknown and set to "missing". Participants with no reported reaction have no duration.

Grade 4 assessment should be made by the investigator using the AE severity grading scale. The assessment will be collected on the AE CRF and thus not reported from the e-diary.

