8.3.4. Reactogenicity Electronic Diary

The participant or participant's parent(s)/legal guardian will be required to complete a reactogenicity e-diary after each vaccination. These participants or participants' parent(s)/legal guardians will be asked to monitor and record local reactions, systemic events, and temperature for 7 days from the day of administration of the study intervention. The reactogenicity e-diary allows recording of these assessments only within a fixed time window, thus providing an accurate representation of the participant's experience at that time. Data on local reactions and systemic events reported in the reactogenicity e-diary will be transferred electronically to a third-party vendor, where they will be continually available for review by investigators, Pfizer clinicians, and other selected study team members via an internet-based portal.

At intervals agreed to by the vendor and Pfizer, these data will be transferred electronically into Pfizer's database for analysis and reporting. These data do not need to be reported by the investigator in the CRF as AEs.

Investigators (or designee) will be required to review the reactogenicity e-diary data online at frequent intervals as part of the ongoing safety review.

The investigator or designee must obtain stop dates from the participant or participant's parent(s)/legal guardian for any reactions ongoing on the last day that the reactogenicity e-diary was completed. The stop dates should be documented in the source documents and the information entered in the CRF.

Please note that all provisioned e-diary devices must be collected at the end of Visit 3 (1-month follow-up visit) per the SoA.

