## 3.1.1.2. Systemic Events Within 7 Days After Vaccination

Systemic events, including fever, fatigue/tiredness, headache, vomiting, diarrhea, muscle pain, and joint pain, are reported from Day 1 through Day 7 after vaccination, where Day 1 is the day of vaccination with RSVpreF or placebo. The derivations for the systemic events as described below will be handled similarly to the way that local reactions are handled for the presence for each participant, severity level, duration, onset day, and presence of systemic event on each and any day.

- 1. Presence (yes or no) of each systemic event on any day (Day 1 through Day 7) after vaccination.
- 2. Presence (yes or no) of any systemic event on any day (Day 1 through Day 7) after vaccination.

- 3. Maximum severity of each systemic event on any day (Day 1 through Day 7) after vaccination.
- 4. Maximum severity of any systemic event on any day (Day 1 through Day 7) after vaccination.
- 5. Duration of each systemic event after vaccination.
- 6. Onset day of each systemic event after vaccination.
- 7. Presence (yes or no) of each systemic event on each and any of the 7 days after vaccination.
- 8. Presence (yes or no) of any systemic event on each and any of the 7 days after vaccination.

The grading scale for systemic events is provided in the protocol. However, the derivation of severity of each systemic event on each day should be based on the maximum severity reported from the e-diary or AE CRF, if data are reported from both sources; or the e-diary alone if not reported from the AE CRF.

Fever is defined as a temperature of  $\geq 100.4^{\circ}\text{F}$  ( $\geq 38.0^{\circ}\text{C}$ ). The highest temperature for each day will be recorded in the e-diary. For reporting purposes, fever will be analyzed using the following temperature ranges:

- Mild ( $\geq$ 38.0 to 38.4°C from the e-diary or mild grade from the AE CRF);
- Moderate (>38.4 to 38.9°C from the e-diary or moderate grade from the AE CRF);
- Severe (>38.9 to 40.0°C from the e-diary or severe grade from the AE CRF);
- Grade 4 (>40.0°C from the e-diary or severe grade from the AE CRF, plus documented >40.0°C via CRF query or other sources).

If a participant reports a fever (or severity of fever) by accident, the correct temperature will be transcribed in a data handling memo to be included in the analysis, and the temperature that is confirmed as incorrect will not be included in the analysis.

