## 6.1.1.2. Supplementary Analysis

To support the assessment of reactogenicity, the endpoints below, as specified in Section 3.1.1.1 and Section 3.1.1.2, will be summarized per the supplemental analysis with the same analysis population:

- Duration (days) of each local reaction and each systemic event after vaccination.
- Onset day of each local reaction and each systemic event after vaccination.
- Presence of each and any local reaction and each and any systemic event, on each of the 7 days and for "any day (Days 1-7)."

The presentation of the results will include a basic descriptive summary without the 95% CIs for each group.

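### A reaction with no known end date loses its whole duration, which tends to shorten the supplementary duration summary; chronic reactions and interrupted diaries have no stated rule

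*SAP*

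**What the plan says.** The SAP section Duration of Each Local Reaction (printed as 3.1.1.3, within 3.1.1.1) counts duration in days from start to resolution, both days included. "Resolution of the event is the last day on which the event is recorded in the e-diary (or AE CRF"), or the CRF end date for a reaction unresolved during the diary period, or the AE stop date, "whichever is longer, unless chronicity is established". Then: "If there is no known end date, the duration will be considered unknown and set to" missing.

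For systemic events, SAP 3.1.1.2 states: "The derivations for the systemic events as described below will be handled similarly to the way that local reactions are handled".

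SAP 6.1.1.2 lists the summary: "Duration (days) of each local reaction and each systemic event after vaccination". It is supplementary, given per group and without confidence intervals. SAP 5.2.2 sets the statistics: n, mean, median, standard deviation, minimum and maximum.

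On data collection, Protocol 8.3.4 says: "The investigator or designee must obtain stop dates from the participant or participant's parent(s)/legal guardian for any reactions ongoing on the last day" of the completed diary. The Schedule of Activities (Protocol 1.3.1) repeats this follow-up at Visits 2, 3 and 4, the last at 175 to 189 days.

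**The concern.** Because stop dates are actively pursued, one clear way for an end date to remain unknown is that the reaction was still present when contact ended. Such a value is not missing at random: the longer a reaction lasts, the more likely it is to outlast observation. The rule discards the whole duration even though the onset and a minimum length are on record.

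Duration supports the assessment of reactogenicity, a primary endpoint of a dose-finding study. The mean and maximum are the statistics most exposed. The SAP plans no minimum duration and no count of ongoing reactions. A reduced n would show that a value is absent, but not that the reaction had still been present.

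**Working it through.** The documents give no reaction rate, duration distribution or rate of unknown end dates, so there is no figure of the plan's own to reproduce. The group size is from SAP 2.3: about 20 children per age, risk and dose group. Everything else below is an assumption.

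**1. One child in a group.** Suppose 10 of 20 children have injection-site pain. Nine resolve after 1, 1, 2, 2, 2, 2, 3, 3 and 3 days (sum 19). The tenth has onset on Day 1, is still in pain on Day 7, and has no later record. The known minimum is 7 − 1 + 1 = 7 days.

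| Handling | n | Mean (days) | Median | Maximum |
|---|---|---|---|---|
| Set to missing | 9 | 19/9 = 2.1 | 2 | 3 |
| Last recorded day taken as resolution | 10 | 26/10 = 2.6 | 2 | 7, shown as exact |
| Right-censored at last documented day | 10 | at least 2.6 | 2 | ≥ 7 |
| Right-censored, if documented as present to Day 30 | 10 | at least 49/10 = 4.9 | 2 | ≥ 30 |

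The mean and maximum move; the median does not.

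**2. How often a group is affected.** If 30 to 70% of 20 children react, there are m = 6 to 14 reactors. With a share q of reactors lacking an end date, the chance of at least one is 1 − (1 − q)^m:

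- q = 2%: 11% (m = 6) to 25% (m = 14)
- q = 5%: 27% to 51%
- q = 10%: 47% to 77%

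**3. Unknown end dates only among long reactions.** Assume lognormal durations rounded up to whole days, median 2 days, log-SD 0.9. The share lasting over 7 days is 1 − Φ(ln(7/2)/0.9) = 1 − Φ(1.39), about 8%. If 10 to 50% of those lack an end date, 20,000 simulated groups per scenario with 6, 10 or 14 reactors give:

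- groups with at least one missing duration: 5 to 44%
- of those, groups that lose their true maximum: 62 to 90%
- mean in affected groups: from about 4.0–4.9 days down to 3.1–3.4
- fall in the median in affected groups: 0.2 to 0.6 day

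With 28 reactors (70% of 40), 40 to 64% of affected groups lose the maximum. These results compare the rule with the true durations. Censoring recovers only the part up to the last documented day.

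**4. What the text leaves open.** A reaction unresolved in the diary period takes its end date from the CRF; if there is none, the missing rule applies. But the same section also names the last recorded day as resolution, and SAP 5.3.1.1 sets missed diary days left unfilled by the AE CRF to no. For a child who stops the diary during a reaction, these can be read as giving a shortened duration counted as resolved. For chronic reactions, the closing exception suspends the resolution rule and puts nothing in its place.

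**The case against.** The strongest reply is that few children will be affected and little depends on them. Stop dates are mandatory and sought for about 6 months. Protocol 7.3 requires repeated contact attempts before a child is declared lost, and Protocol 7.2 lets a child who stops study procedures stay in AE monitoring. Some unknown end dates will simply be forgotten dates of resolved reactions. Incidence and maximum severity, the main reactogenicity results in SAP 6.1.1.1, still count the child. Withdrawals are tabulated with reasons (SAP 6.5.2), no hypothesis is tested, and no stopping rule uses duration. All of this stands and keeps the point minor. It does not supply the missing minimum duration or the count of ongoing reactions.

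A reader might infer more than the text supports:

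- **That every chronic reaction drops out.** The SAP says only "whichever is longer, unless chronicity is established" and gives no replacement rule. A chronic reaction with a recorded stop date is not covered by the missing rule.
- **That every withdrawn or lost child drops out.** The stop date may already have been collected, or the last-recorded-day wording may give a truncated value.
- **That the longest value is always lost.** It is a tendency, as step 3 shows.
- **That a dose level would look better tolerated overall.** Only the supplementary duration table is affected.

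**Conclusion.** The point holds as a minor, inexpensive improvement. Setting the duration to missing when the end date is unknown tends to bias mean and maximum duration downward, because reactions still present at last contact are among those removed. Truncation, where it applies instead, also understates duration and presents it as resolved. The text does not settle which of the two applies to a diary that stops mid-reaction, or what applies to chronic reactions.

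The direction rests on at least some unknown end dates belonging to reactions that outlasted observation. The documents do not say what share that is. The sizes shown are illustrations under assumed rates, not predictions for this study.

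**What to change.** Replace the missing rule in the SAP duration section with: *If the end date is unknown or the reaction is ongoing at last contact, duration is reported as at least the number of days from onset to the last day the reaction is documented as present (right-censored).* Then:

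- Apply the same rule when the diary stops during a reaction, and to chronic reactions without a stop date.
- Report per group the number of reactions with an ongoing or unknown end date.
- Show the maximum as ≥ x days where it is censored.
- Apply all of this to systemic events.

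The censoring date should be the last day documented as present, because neither document shows that a later last-symptomatic date is always collected. For some children this will be only the last diary day. A median that accounts for censoring is optional.

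The cost is one derived flag and one extra table line; no new data collection is needed. The downside for the sponsor is that reported durations may be slightly less favourable.
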